14 STATISTICAL ANALYSIS METHODS

The methods of analysis to be used for both objectives of the study and for description of the study variables are detailed below.

Quantitative variables will be described with measures of central tendency and dispersion: mean, median, SD (standard deviation), Q1 (first quartile) and Q3 (third quartile), minimum and maximum. Qualitative variables will be described using absolute and relative frequencies.

In the descriptive analysis of qualitative variables, two percentage columns will be presented, total percentage (%) and valid percentage (% valid), that are respectively, the percentage over the sum of valid responses plus missing values and the percentage over the total of valid responses.

Clopper-Pearson confidence intervals at 95.0% will be shown for the primary and secondary objectives.

For time-to-event variables (i.e. fracture free-survival) will be analysed using the Kaplan-Meier method. The median and the 95% CI as well as the number of events and patients censored will be provided. Error standard will be estimated per the method Greenwood (Greenwood, 1926). KM graphs will be presented along with the number of case-at-risk at exact time points.

Change in Gillette Functional Assessment Questionnaire from Screening to 1 year follow up will be analysed by means of descriptive statistics as a continuous variable. Comparisons will be performed by means of paired t-test (parametric) or Wilcoxon (non-parametric) depending on the distribution of the sample.

These tests will be used in all bilateral cases and with a level of significance of 0.05. In cases where a p-value less than 0.05 appears, it refers to the existence of statistical significance.

No imputation for missing data will be considered.

No adjustment for multiple comparisons will be performed.

Data will be analysed using SPSS v29.0 or later.

Interim Analysis: No interim analysis is planned.

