7.2 Subjects and Sites Numbers

This study will be conducted only on patients with a regular indication for JTIN as per IFU (no off-label use will be included): the nail is indicated for fractures, osteotomies, malunions and non-unions in femur and tibia in pediatric patients suffering from osteogenesis imperfecta. The JTIN is intended to be used in pediatric patients, older than 18 months.

This study includes only one site (monocentric) located in Paris, France. The site was chosen for this study due to the number of subject devices already implanted, and the wideness of the indications covered by the surgeries. The site was also positively evaluated by sponsor for the appropriate qualification and competency of the investigator and of the staff, and availability of facilities and equipment.

The enrollment objective for this study is of 20 evaluable cases (i.e. procedures, see paragraph "Determination of the Sample Size"). For the purposes of this study, a case is defined as one implanted JTIN nail in one treated bone. Each case can be evaluated and recorded from implantation to the last visit for this study (see "Visits and Assessments Schedule" table and "Procedure" paragraph) or up to implant removal if this happens before the last visit. For each case one eCRF record will be created (see "Subject Identifier" paragraph).

Therefore, a single patient at the clinical site can contribute for more than one case e.g.: a patient can have several JTIN each implanted in a different bone, or can have more JTIN implanted in the same bone but at different times.

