12.3 Determination of the Sample Size

Due to the observational nature of the study, no formal sample size calculation has been done, but a revision of the literature on the complication rates (intended as at least one serious/not serious adverse event certainly or possibly related to the procedure up to 1 year follow-up) has been made. The scientific literature reports that the percentage of procedures which develop at least one serious/not serious adverse event certainly or possibly related to the procedure itself is between 9% and 60%, with a mean of 31%. Assuming a complication rate aligned or better than the mean observed in literature (31%), a sample size of 15 procedures will be sufficient to estimate the adverse event rate with the upper limit of the 95% confidence interval equal or lower than the worst complication rate seen in literature (i.e. 60%).

Starting from this sample size, to also assume that the success rate (intended as proportion of procedures that result in a bone union achieved) is aligned or better than the mean observed in literature (80%), 20 procedures will be needed.

Considering a drop-out or a non-evaluable rate of 20% of the procedures, a total of approximately 25 procedures should be made. Each subject could have from 1 to 4 procedures. Assuming the worst scenario of no more than 1 procedure for subjects, a maximum of 25 subjects needs to be enrolled. Anyway, the enrolment will stop when the total number of the procedures is reached.

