23.1 ADVERSE EVENTS

The categorical variables to be described are, N and (%) and Clopper-Pearson confidence intervals will be shown at 95.0% as well, for the overall population and for subgroups of patients defined according to OI Type Diagnosis (Mild/Non-deforming / Severe / Highly Severe/Progressively deforming / Lethal) as defined in section 15.6 of this document:

- Patients with at least one adverse event
- Patients with at least one serious adverse event
- Patients with at least one related adverse event (considering related as Yes, certainly related and Yes, possibly)
- Patients with at least one serious related adverse event (considering related as Yes, certainly related and Yes, possibly)
- Procedures with at least one adverse event
- Procedures with at least one serious adverse event
- Procedures with at least one related adverse event (considering related as Yes, certainly related and Yes, possibly)
- Procedures with at least one serious related adverse event considering related as Yes, certainly related and Yes, possibly)

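### The procedure-level 95% intervals assume independent nails, although one child may contribute up to four; if outcomes within a child are positively correlated, the intervals are too narrow

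*SAP*

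**What the plan says.** The unit of analysis is the nail. In protocol 7.2, "a case is defined as one implanted JTIN nail in one treated bone", and "a patient can have several JTIN each implanted in a different bone"; the same section also allows further nails in one bone at different times. Protocol 12.3 and SAP 9 put the number at one to four per child.

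For the analysis, SAP 14 says "Clopper-Pearson confidence intervals at 95.0% will be shown for the primary and secondary objectives". SAP 23.1 applies this to the primary endpoint at nail level: "Procedures with at least one related adverse event (considering related as Yes, certainly related and Yes, possibly". SAP 24.1 to 24.3 do the same for nail removal, bone union and fracture. The Kaplan-Meier standard error in SAP 14 is plain Greenwood, with time defined per procedure in SAP 24.3.

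The SAP is aware that nails share children. SAP 15.3 tabulates procedures per patient, and the note in SAP 16.1 deals with several implants in one operation, but only for surgery time and radiation dose. SAP 23.1, 23.2, 24.2 and 24.3 also give patient-level counts with intervals. SAP 24.1 (implant survival) does not. Neither document plans a clustered interval, a model with a child effect or a one-nail-per-child analysis.

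**The concern.** A Clopper-Pearson interval is valid when each unit is an independent trial. Nails in one child share the OI type and the child's bone fragility, and often the operation, so positive correlation is the natural expectation. The SAP itself splits every main outcome by OI type, which is a property of the child. Twenty nails from five children then carry less information than twenty nails from twenty children, but the planned interval is the same in both cases.

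The study is descriptive, so the interval is the main statement of uncertainty on the primary safety result. Protocol 12.3 also justifies its base sample size by the upper limit of that interval.

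**Working it through.** **Inputs from the documents.** Rate 31%, target upper limit 60%, 15 procedures, bone union 80%, 20 evaluable procedures, 20% dropout, 25 in total, one to four procedures per child (protocol 12.3); two-sided 95% Clopper-Pearson (SAP 14). **Assumed:** the number of nails per child and the within-child correlation (ICC). The documents give neither.

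**1. The plan's own figures.** Upper limit = 0.975 quantile of Beta(x+1, n−x), with x = 0.31n.
- n = 14, x = 4.34: 60.5%.
- n = 15, x = 4.65: 59.4%.

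So 15 is the smallest number that meets 60%, with 0.6 points to spare, under independence. Dropout: 20/(1 − 0.20) = 25. The 20 for bone union cannot be tested because 12.3 states no precision criterion; 16/20 gives 56.3% to 94.3%.

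**2. Effective sample size for 20 nails.** Design effect = 1 + (m − 1) × ICC, where m = Σ(nails²)/Σ(nails).
- Ten children × 2: m = 40/20 = 2.
- Eight children with 4, 4, 3, 3, 2, 2, 1, 1: m = 60/20 = 3.
- Five children × 4: m = 80/20 = 4.

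Effective n = 20/design effect, and the last column is Clopper-Pearson at that n and 31%.

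| Layout | ICC | Design effect | Effective n | Interval at 31% |
|---|---|---|---|---|
| 20 × 1 | any | 1.00 | 20.0 | 12.6% to 55.3% |
| 10 × 2 | 0.3 | 1.30 | 15.4 | 10.6% to 59.0% |
| 10 × 2 | 0.5 | 1.50 | 13.3 | 9.4% to 61.2% |
| Eight children | 0.3 | 1.60 | 12.5 | 8.9% to 62.3% |
| Eight children | 0.5 | 2.00 | 10.0 | 7.2% to 66.1% |
| 5 × 4 | 0.3 | 1.90 | 10.5 | 7.6% to 65.2% |
| 5 × 4 | 0.5 | 2.50 | 8.0 | 5.5% to 70.3% |

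The SAP would print the first row in every case.

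**3. Actual coverage of the planned interval.** Each child's count is beta-binomial with parameters 0.31(1/ICC − 1) and 0.69(1/ICC − 1). The counts are convolved over children, and the probability is summed over totals whose Clopper-Pearson interval on 20 nails contains 31%. The last column is the chance that the upper limit lies below the true rate (nominal 2.5%).

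| Layout | ICC | Coverage | Upper limit too low |
|---|---|---|---|
| 20 × 1 | any | 97.2% | 0.6% |
| 10 × 2 | 0.3 | 94.7% | 1.4% |
| 10 × 2 | 0.5 | 92.8% | 2.1% |
| Eight children | 0.3 | 91.9% | 2.3% |
| Eight children | 0.5 | 87.9% | 4.1% |
| 5 × 4 | 0.3 | 88.9% | 3.7% |
| 5 × 4 | 0.5 | 82.6% | 7.0% |

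Coverage drops below 95% at an ICC of about 0.27 with two nails each and about 0.09 with four each. If only five children have two nails and the rest one, it stays at or above 95% up to ICC 0.5. For bone union at 80%, coverage at ICC 0.3 and 0.5 is 95.5% and 93.3% (10 × 2), and 89.7% and 82.4% (5 × 4), against 97.8% under independence.

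**4. The figure of 15 under clustering, at ICC 0.1.**
- Seven children with two nails and one with one: m = 29/15 = 1.93, effective n 13.7, upper limit 60.8%.
- Nails 4, 4, 4, 3: m = 57/15 = 3.8, effective n 11.7, upper limit 63.4%.

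Both miss 60%. The 20 evaluable procedures give some slack: 10 × 2 at ICC 0.3 still reaches 59.0%.

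The effect on the Greenwood limits follows from the same independence assumption; it was not quantified.

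**The case against.** **Patient-level intervals are planned.** They avoid the clustering, but they estimate the chance of any event across all of a child's nails, not the rate per nail that defines the primary endpoint. Implant survival has no patient-level version. This softens the point without removing it.

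**The shortfall depends on unknown inputs.** This stands. The exact interval is conservative and absorbs modest correlation. The large shortfalls need several nails per child and an ICC of 0.3 to 0.5.

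**A reader might infer that the upper limit for related events is always materially too low.** The figures do not support that. At 31%, most misses in every scenario are lower limits that are too high. The upper-limit error clearly exceeds 2.5% only in the eight-child layout at ICC 0.5 and the five-child layout at 0.3 and above.

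**A reader might infer that a conclusion turns on comparing the interval with 31% or 60%.** No decision rule uses either. Both are planning values in a section that says "no formal sample size calculation has been done", and the planned comparison with other devices is visual and concerns the secondary variables.

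**A reader might infer that protocol 12.3 mistakes the best case for precision for the worst.** The text is "Each subject could have from 1 to 4 procedures. Assuming the worst scenario of no more than 1 procedure for subjects", and it leads to a maximum of 25 subjects. As a bound on recruitment that is correct, and it makes no claim about precision. What 12.3 leaves out is that its precision argument assumes independent procedures.

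**Conclusion.** The point holds in conditional form and should be fixed. The planned procedure-level intervals ignore a clustering that the plan itself expects. If within-child correlation is positive, they are narrower than their stated confidence allows: slightly with two nails per child and ICC 0.3, and by 6 to 12 percentage points below nominal with four per child at ICC 0.3 to 0.5 (95 − 88.9 = 6.1; 95 − 82.6 = 12.4). The margin behind the 15 procedures is lost at ICC 0.1 once most children have two nails.

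These sizes rest on a beta-binomial model with assumed layouts and correlations. The point estimates are unaffected.

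**What to change.** - **SAP 14, 23.1 and 24.1 to 24.3, overall procedure-level rates:** keep the point estimates and report a child-clustered 95% interval. One workable form is Clopper-Pearson on the effective sample size, with the variance clustered on child, capped at the number of nails, and using the number of children when there are no events or all events. Show the number of children beside each rate.
- **Sensitivity analysis:** first nail per child with the plain exact interval, with a preset rule for choosing among nails implanted on the same day.
- **OI-type subgroups:** show counts of nails and children, and label any plain interval as assuming independence. There will be too few children for a stable clustered variance.
- **Kaplan-Meier:** use a child-clustered variance, or run the curve on the first nail per child.
- **Protocol 12.3 and SAP 9:** keep the recruitment sentence. Add that the precision behind 15 procedures assumes independent procedures (one nail per child) and falls as nails per child rise.

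The cost is SAP wording and a short script. The link between a child's records already exists through the reference to the first ID (protocol 7.4.2 and 10.2.1), and SAP 16.1 already matches cases by patient.

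The intervals become wider: mean width about 0.56 instead of 0.41 for eight children at ICC 0.3. With five children and four nails each it is 0.55 at ICC 0 and 0.68 at ICC 0.3, so the clustered interval is conservative when children are very few. The first-nail analysis is offered alongside it for that reason.

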15 DESCRIPTIVE STATISTICAL ANALYSIS

15.1 PATIENT DISPOSITION

A summary of patients included in the study, as well as those who are in each populations and the reasons for not belonging to one of the populations will be shown.

15.2 SCREENING AND ENROLMENT VISIT

15.3 DEMOGRAPHICS DATA BY PATIENT

This analysis will be performed on FAS population.

The categorical variables to be described are, N and (%):

- Number of procedures by patient
- Gender (Male / Female)

The descriptive statistic (Mean, SD, Median, Q₁, Q₃, Min, Max) will be shown for the following continuous variables:

- Age at surgery (calculated, in months, as date of surgery minus date of birth (year, month)) by patient at the first procedure
- Age at ICF signature (calculated, in months, as date of ICF signature minus date of birth (year, month)) by patient at the first procedure
- Height by patient at the first procedure
- Weight by patient at the first procedure
- BMI by patient at the first procedure

15.4 DEMOGRAPHICS DATA BY PROCEDURE

This analysis will be performed on FAIS population.

The descriptive statistic (Mean, SD, Median, Q₁, Q₃, Min, Max) will be shown for the following continuous variables:

- Age at surgery (calculated, in months, as date of surgery minus date of birth (year, month))
- Age at ICF signature (calculated, in months, as date of ICF signature minus date of birth (year, month))
- Height
- Weight
- BMI

The categorical variables to be described are, N and (%):

- Gender (Male / Female)

15.5 MEDICAL CONDITIONS BY PATIENT

This analysis will be performed on FAS population.

The categorical variables to be described are, N and (%):

- Medical conditions by patient (Number of patients with **at least one**: (Yes / No)):
 - Autism spectrum disorder
 - Sickle cell disease (SCD)
 - Transient synovitis
 - Septic arthritis
 - Juvenile idiopathic arthritis
 - Cerebral palsy
 - Slipped Capital Femoral Epiphysis (SCFE)
 - Developmental Dysplasia of the Hip (DDH)
 - Blount's Disease
 - Neurogenic Hip Dysplasia
 - Ligamentary laxity
 - Legg–Calvé–Perthes disease
 - Spina bifida
 - Down Syndrome
 - Chromosomal aberration
 - Other (a list will be shown)
 - None
 - History of cardiovascular disease
 - History of diabetes

The categorical variables to be described are, N and (%):

- Family history of disease by patient (Number of patients with **at least one**: (Yes / No)):
 - Osteogenesis imperfecta
 - (Cardio)myopathy
 - Encephalopathy
 - Diabetes Mellitus
 - Hypertension/Cardiovascular disease
 - Thrombosis
 - Malignancy
 - Deafness
 - Renal disease
 - None of the above
 - Unknown

15.6 DIAGNOSIS & X-RAY IMAGES BY PROCEDURE

This analysis will be performed on FAIS population.

The categorical variables to be described are, N and (%):

- OI Type Diagnosis (Type I / Type II / Type III / Type IV / Type V / Type VI / Type VII / Type VIII)
- OI Type Diagnosis groups. A new variable will be calculated according to the following criteria*:
 - Mild/Non-deforming (Type I);
 - Severe (Type IV; Type V, Type VI);
 - Highly Severe/Progressively deforming (Type III, Type VII, Type VIII)
 - Lethal (Type II);

*References: <https://www.niams.nih.gov/health-topics/osteogenesis-imperfecta> and <https://pmc.ncbi.nlm.nih.gov/articles/PMC4314691/#tbl1>.

- Treated bone (Femur / Tibia)
- Body side (Left / Right)
- Body side (Only Left / Only Right / Both). A new variable will be generated based on original variable body side. For procedures with only left, with only right and with both the variable “Treated bone (Femur / Tibia)” will be described separately.
- Intended use of JTIN for this case (Fracture treatment / Osteotomy fixation (e.g. for deformity correction, bone reinforcement) / Malunion treatment / Non-union treatment)
- Was in the bone another fixation device, before JTIN application? (Yes / No)
- Was a software used during pre-planning ? (Yes / No)
 - In case yes, Which software?
 - In case yes, What information you looked for on the software?
 - In case no, Is there a particular reason why a software was not used?
- Preoperative AP projection X-Ray
- Preoperative ML projection X-Ray
- Number of additional radiographic images to upload (1 / 2)

The descriptive statistic (Mean, SD, Median, Q₁, Q₃, Min, Max) will be shown for the following continuous variables:

- Time from date of fracture to Date of screening visit (calculated as Date of screening visit minus date of fracture)
- Time from date of fracture to surgery (calculated as date of surgery minus date of fracture)

15.7 PRE-OP CLINICAL EXAMINATION AND GILLETTE SCORE BY PROCEDURE

This analysis will be performed on FAIS population.

The categorical variables to be described are, N and (%):

- The patient can stand up? (Yes / No (Non-weight-bearing)), if 'Yes':
 - Pre operative Weight-bearing Protocol (if not prescribed by surgeon, report what is known) (Toe-touch weight-bearing (TTWB) / Partial weight-bearing (PWB)/ Full weight-bearing (FWB)
 - The patient walks? (Yes / No)
- How frequent did the patient reported pain at the affected limb before JTIN application? (Never / Some of the days / About half of the days / Most of the days /Everyday), is not equal to 'Never' VAS Pain Score according to the patient will be described (Mean, SD, Median, Q₁, Q₃, Min, Max)
- Was the pain pharmacologically treated? (Yes / No / unknown)
- Was the Gillet Score performed BEFORE the treatment with JTIN? (Yes / No) is equal to 'Yes' Gillette Functional Assessment Questionnaire result will be described (Mean, SD, Median, Q₁, Q₃, Min, Max)

15.8 PRE-OP ROM

This analysis will be performed on FAIS population.

The categorical variables to be described are, N and (%):

- Which Range of Motion are available for this patient?
 - None
 - Knee Flexion
 - Knee Extension
 - Hip Flexion
 - Hip Extension
 - Hip Abduction
 - Hip Internal Rotation (supine)
 - Hip External Rotation (supine)
 - Ankle Joint Dorsiflexion
 - Ankle Joint Plantarflexion

The descriptive statistic (Mean, SD, Median, Q₁, Q₃, Min, Max) will be shown for the following continuous variables:

- ROM Knee Flexion

- ROM Knee Extension
- ROM Hip Flexion
- ROM Hip Extension
- ROM Hip Abduction
- ROM Hip Internal Rotation (supine)
- ROM Hip External Rotation (supine)
- ROM Ankle Joint Dorsiflexion
- ROM Ankle Joint Plantarflexion

16 SURGERY VISIT

This analysis will be performed on FAIS population.

16.1 DEVICE APPLICATION SURGERY

The descriptive statistic (Mean, SD, Median, Q₁, Q₃, Min, Max) will be shown for the following continuous variable:

- Duration of the surgery (hours)

The categorical variables to be described are, N and (%):

- Was other fixation device removed from the same bone during this surgery? (Revision surgery) (Yes / No), if yes:
 - What device was removed? :
 - JTIN nail
 - Other telescopic nail
 - Non-telescopic rigid nail
 - Elastic nails
 - Plate
 - Screws
 - Other (a list will be shown)

The descriptive statistic (Mean, SD, Median, Q₁, Q₃, Min, Max) will be shown for the following continuous variables:

- Female rod diameter mm
- Diameter mm x 10
- Nail length mm
- Number length

The categorical variables to be described are, N and (%):

- Nail Product Code
 - 99-67735100
 - 99-67735120
 - 99-67735130
 - 99-67735140
 - 99-67735150
 - 99-67740130
 - 99-67740155
 - 99-67740180
 - 99-67740205
 - 99-67740230
 - 99-67745160
 - 99-67745175
 - 99-67745190
 - 99-67745205
 - 99-67745230
 - 99-67750250
 - 99-67750275
 - 99-67750300
 - 99-67750325
 - 99-67750350
 - 99-67760250
 - 99-67760275
 - 99-67760300
 - 99-67760325
 - 99-67760350
- If 'Nail Product Code' is equal to '99-67735100' answer this question:
 - Nail batch number (B1783051 / B2641703 / B3009814)
- If 'Nail Product Code' is equal to '99-67735120' answer this question:
 - Nail batch number (B1782950 / B2641683 / B2742622 / B4443378)
- If 'Nail Product Code' is equal to '99-67735130' answer this question:
 - Nail batch number (B1786577 / B1788041 / B2641704 / B2815658)
- If 'Nail Product Code' is equal to '99-67735140' answer this question:
 - Nail batch number (B1786575 / B1788107 / B2641702 / B3478907 / B3549910)
- If 'Nail Product Code' is equal to '99-67735150' answer this question:

- Nail batch number (B1783016 / B1788040 / B2641701 / B2992850 / B4443379)
- If 'Nail Product Code' is equal to '99-67740130' answer this question:
 - Nail batch number (B1786576 / B1788109 / B1803399)
- If 'Nail Product Code' is equal to '99-67740155' answer this question:
 - Nail batch number (B1782964 / B1788110 / B1808958 / B2598629)
- If 'Nail Product Code' is equal to '99-67740180' answer this question:
 - Nail batch number (B1786609 / B1788104 / B1808957 / B2598628 / B2959917 / B3013876 / B3584086 / B3935695)
- If 'Nail Product Code' is equal to '99-67740205' answer this question:
 - Nail batch number (B1786622 / B1788105 / B2588616 / B3560929 / B4443313)
- If 'Nail Product Code' is equal to '99-67740230' answer this question:
 - Nail batch number (B1786621 / B1788039 / B1795858 / B3138829 / B3372939)
- If 'Nail Product Code' is equal to '99-67745160' answer this question:
 - Nail batch number (B1795495 / B2319444 / B2452597)
- If 'Nail Product Code' is equal to '99-67745175' answer this question:
 - Nail batch number (B1843786 / B2304454 / B2669626)
- If 'Nail Product Code' is equal to '99-67745190' answer this question:
 - Nail batch number (B1796858 / B2319443 / B2815657 / B3439975 / B4185631)
- If 'Nail Product Code' is equal to '99-67745205' answer this question:
 - Nail batch number (B1796857 / B3013875 / B4443312)
- If 'Nail Product Code' is equal to '99-67745230' answer this question:
 - Nail batch number (B1788625 / B1795239 / B1811305 / B3905681)
- If 'Nail Product Code' is equal to '99-67750250' answer this question:
 - Nail batch number (B1788627 / B2452596 / B2626613)
- If 'Nail Product Code' is equal to '99-67750275' answer this question:
 - Nail batch number (B1788629 / B1808956 / B2624778 / B3138828)
- If 'Nail Product Code' is equal to '99-67750300' answer this question:
 - Nail batch number (B1788628 / B1808850 / B3175772)
- If 'Nail Product Code' is equal to '99-67750325' answer this question:
 - Nail batch number (B1803398 / B3352050)
- If 'Nail Product Code' is equal to '99-67750350' answer this question:
 - Nail batch number (B1801940 / B2343541)
- If 'Nail Product Code' is equal to '99-67760250' answer this question:
 - Nail batch number (B2299500)
- If 'Nail Product Code' is equal to '99-67760275' answer this question:
 - Nail batch number (B2299495)

- If 'Nail Product Code' is equal to '99-67760300' answer this question:
 - Nail batch number (B1801939)
- If 'Nail Product Code' is equal to '99-67760325' answer this question:
 - Nail batch number (B1808849 / B3175768)
- If 'Nail Product Code' is equal to '99-67760350' answer this question:
 - Nail batch number (B1801938 / B3325975)
- Did the patient receive a blood transfusion? (Yes / No), if Yes:
 - How many BT unit were used, Mean, SD, Median, Q₁, Q₃, Min, Max will be described

The descriptive statistic (Mean, SD, Median, Q₁, Q₃, Min, Max) will be shown for the following continuous variables:

- How many x-ray images were taken?
- Radiant dose (Gy)

The categorical variables to be described are, N and (%):

- According to the investigator, was the objective of the surgery achieved? (Yes / No / Partially), if not or partially:
 - Please explain your answer and clarify what should be done to fulfil the treatment
 - Is another surgery recommended? (Yes / No), if yes:
 - Why is another surgery recommended?

Note.- Some patients may receive multiple implants during the same surgery. The use of multiple nails can affect surgery time and radiation dose. If multiple implants were used will be determined by identifying cases with the same patient ID and surgery date.

- The number of implants used in the same surgery will be shown (n,%)

In addition, the descriptive statistic (Mean, SD, Median, Q₁, Q₃, Min, Max) will be shown for the following continuous variables based on the number of implants used in the same surgery:

- Radiant dose (Gy). The mean of the values reported for implants with the same date of surgery will be provided.
- Duration of the surgery (hours). The mean of the values reported for implants with the same date of surgery will be provided.

